2.6. DETERMINATION OF SAMPLE SIZE

The sample size calculation for this trial is based on the effect achieved in the teduglutide Phase 3 trial and that the PS volume changes from baseline after 24 weeks of treatment (primary endpoint) are expected to be -4.5 L/week and -4.3 L/week with twice-weekly and once-weekly dosing, respectively, and -2.3 L/week for placebo. The standard deviation of the treatment effect (once-weekly or twice-weekly versus placebo) is assumed to be 2.62. A total of 101-112 SBS patients are planned for inclusion, with 33-37 patients planned for each of the three treatment groups. The trial size will result in 93-95% power for detecting the assumed difference with either once-weekly or twice-weekly for the primary endpoint. The assumed effects include imputed effects for patients with missing data. The power calculations are shown in Table 1 including the scenario where once-weekly and twice-weekly dosing are assumed to be slightly worse.

Table 1 Power considerations

Power (%) to show superiority of either once-weekly or twice-weekly compared to placebo with respect to the
primary endpoint

Assumptions:			Number of patie	ents (total)		
PS vol, change from baseline (L/week)						
Twice-weekly One-weekly Placebo		99	108	117	129	
-4.5	-4.3	-2.3	93	95	96	98
-4.3	-4.1	-2.3	88	91	93	95

The two comparisons, once-weekly vs placebo and twice-weekly vs placebo are tested two-sided in parallel at α =0.025 to control the overall type 1 error at 5% level.

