3.2. KEY SECONDARY EFFICACY ENDPOINTS

The following 4 key secondary efficacy endpoints will be analyzed to assess the treatment effect using the FAS. The key secondary endpoints will be derived based on the actual weekly PS volume or the number of days on actual PS a week, using the selected valid 7-day period at Week 12, 20, and 24, respectively. For details on the derivation see Appendix A.

First key secondary efficacy endpoint: Clinical response, defined as at least 20% reduction in actual weekly PS volume from baseline to both Weeks 20 and 24

The primary estimand will handle the intercurrent event of treatment discontinuation under a 'composite strategy', i.e. incorporating the intercurrent event in the response definition. For patients who discontinue treatment prematurely, a non-response will be imputed, indicating failure to randomized treatment. This assesses the treatment effect of

• Difference in percentage of clinical response without treatment discontinuation between glepaglutide treatment group and placebo in the SBS population.

Missing data for other reasons will be imputed with a non-response.

The difference in clinical response rates between each glepaglutide group and the placebo will be calculated using Mantel-Haenszel weighing and presented with 95% confidence intervals (using the Wald estimation method). Whether the difference equals zero will be tested using the Cochran-Mantel-Haenszel (CMH) adjusted for the stratification factor. In the presence of strata with zero counts in the crosstabulation between stratification factor and treatment, an unadjusted difference in clinical response rates between each glepaglutide group and the placebo will be calculated (i.e. without stratification), to avoid inappropriate weighing of the risk differences in each stratum. The null hypothesis of a difference equals zero will still be tested using the Cochran-Mantel-Haenszel (CMH), with a single contingency table.

As a sensitivity analysis of the primary estimand of first key secondary efficacy endpoint, the actual weekly PS volume will be derived using a valid 14-day period prior to the visit. For details on the derivation of actual weekly PS volume within a 14-day period, see Appendix A. Handling of missing data and analysis of this endpoint will follow that of the primary estimand of first key secondary efficacy endpoint.

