In addition, a supplementary estimand will be included using a 'treatment policy strategy' assessing the treatment effect of

• Difference in percentage of clinical response between glepaglutide treatment group and placebo in the SBS population, regardless of whether treatment is discontinued.

Response status will be derived from the CR-imputed data sets generated from the multiple imputation approach described for the primary estimand (main estimator) of the primary efficacy endpoint. The difference will be analysed in the same way as the primary analysis of first key secondary efficacy endpoint. The test statistics based on the MI will be combined by applying Rubin's rule after Wilson-Hilferty transformation (Wilson et al 1931).

25 August 2022

To get an overview of the different estimands and estimators for the binary key secondary efficacy endpoints, and how missing data will be handled, please see Table 6.

Second key secondary efficacy endpoint: Reduction in days on $PS \ge 1$ day/week from baseline to Week 24

The same estimands (main estimators) and sensitivity estimator will be investigated, as for the first key secondary efficacy endpoint (see Table 6). The same analysis method will be applied as well.

Primary 'composite' estimand for the second key secondary efficacy endpoint

• Difference in percentage of reduction in days on $PS \ge 1$ day/week from baseline to Week 24 without treatment discontinuation between glepaglutide treatment group and placebo in the SBS population.

Supplementary 'treatment policy' estimand for the second key secondary efficacy endpoint

• Difference in percentage of reduction in days on $PS \ge 1$ day/week from baseline to Week 24 between glepaglutide treatment group and placebo in the SBS population, regardless of whether treatment is discontinued.

For the supplementary estimand, response status is derived using the same MI model as for primary analysis of primary efficacy endpoint with the number of PS days as dependent variable.

Third key secondary efficacy endpoint: Change in actual weekly PS volume from baseline to Week 12

The same estimands (main estimators) and sensitivity estimators will be investigated, as for the primary efficacy endpoint (see Table 3). The same analysis method will be applied as well (see 3.1).

Primary 'treatment policy' estimand for the third key secondary efficacy endpoint

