• Difference between mean change from baseline in actual weekly PS volume at 12 weeks in the SBS population regardless of whether treatment is discontinued.

Supplementary 'hypothetical' estimand for the third key secondary efficacy endpoint

• Difference between mean change from baseline in actual weekly PS volume at 12 weeks in the SBS population, as if treatment discontinuation never occurred.

Fourth key secondary efficacy endpoint: Reduction in weekly PS volume of 100% (weaned off) at Week 24

The same estimands (main estimators) and sensitivity estimator will be investigated, as for the first key secondary efficacy endpoint (see Table 6). The same analysis method will be applied as well.

Primary 'composite' estimand for the fourth key secondary efficacy endpoint

25 August 2022

• Difference in percentage of reduction in weekly PS volume of 100% (weaned off) at Week 24 without treatment discontinuation between glepaglutide treatment group and placebo in the SBS population.

Supplementary 'treatment policy' estimand for the fourth key secondary efficacy endpoint

• Difference in percentage of reduction in weekly PS volume of 100% (weaned off) at Week 24 between glepaglutide treatment group and placebo in the SBS population, regardless of whether treatment is discontinued.

Note, the main analyses of the primary estimands follow the treatment policy strategy for the primary and third key secondary endpoints and the composite strategy for the first, second and forth key secondary endpoint. This is according to the confirmatory testing strategy described in the protocol version 10.0.

Table 6 Overview of estimands and handling of missing data for binary key secondary efficacy endpoints

Intercurrent event	Data observed or missing	Primary estimand 'Composite'		Supplementary estimand 'Treatment policy'
		Main estimator	Sensitivity estimator – PS vol derived based on 14-day period	Main estimator
Prematurely discontinuation of IMP	Observed	Non-response	Non-response	Value used as observed
	Missing	Non-response	Non-response	Response status derived from MI (CR Placebo)*
No prematurely discontinuation of IMP	Observed	Value used as observed	Value used as observed	Value used as observed
	Missing	Non-response	Non-response	Response status derived from MI (CR Placebo)*

Abbreviations: MI = multiple imputation, CR = copy reference

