Depending upon the results for the first three endpoints in the regimen where the procedure begins, the significance level is specified for the other regimen at $\alpha/2$ or at α . The sequential testing procedure then continues for the first three endpoints in the other regimen. If all six hypotheses (three first endpoints from both regimens) are significant, the last two key secondary endpoints are evaluated sequentially at the α significance level, only continuing to the next evaluation if the preceding is statistically significant. The parallel gatekeeping procedure is displayed below in Figure 1.

Figure 1 Testing hierarchy

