Reduction of at least 30% in actual weekly PS volume from baseline to both Weeks 20 and 24

The difference in response in reduction of $\geq 30\%$ in PS volume from baseline to both Weeks 20 and 24 between each glepaglutide treatment group comparison to placebo will be tested using the CMH test adjusted for the stratification factor will be analyzed in a similar manner as the clinical response endpoint (first key secondary endpoint).

Reduction in prescribed weekly PS volume of 100% (weaned off) at Week 24

The difference in response in prescribed weekly PS volume of 100% (weaned off) at Week 24 between each glepaglutide treatment group comparison to placebo will be tested using the CMH test adjusted for the stratification factor will be analyzed in a similar manner as the weaned off endpoint based on actual PS volume (fourth key secondary endpoint).

PGIC improvement at weeks 4, 12, 20, and 24

PGIC improvement is defined as responding "Very Much Improved" or "Much Improved" on a 7-point Likert Scale for each of the weeks 4, 12, 20, and 24. Improvement between each glepaglutide treatment regimen compared to placebo will be tested by week, using the CMH test adjusted for the stratification factor. In similar fashion, improvement between each glepaglutide treatment regimen versus placebo will be tested using collapsed categories of Improvement, No Change, and Worsening, where Improvement is defined as a response of "Very Much Improved" or "Much Improved" or "Minimally Improved", and No Change is defined as the response of "No Change", and Worsening is defined as a response of "Minimally Worse" or "Much Worse" or "Very Much Worse". Improvement using collapsed 25 August 2022 Confidential Page 24 of 65

categories between each glepaglutide treatment regimen compared to placebo will tested by week using a Mantel-Haenszel chi-squared test for ordered categories. No imputation for missing values will be performed.

Change in weight from baseline to Week 24

The change in body weight (kg) from baseline to Week 24 will be presented descriptively by baseline BMI subgroup. Descriptive statistics will include the number of non-missing observations, mean, SD, median, minimum, and maximum values. A shift table by BMI subgroup from baseline to Week 24 will be presented. The BMI subgroups are defined as: <18.5 kg/m2, \geq 18.5 to <25 kg/m2, \geq 25 to <30 kg/m2 and \geq 30 kg/m2.

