3.5. OTHER EFFICACY ENDPOINTS

The following other efficacy endpoints will be summarized to assess the treatment effect using the FAS.

The endpoints related to the number of days on actual PS a week will be derived using the selected valid 7-day period used for the primary endpoint. Additionally to summary statistics, these endpoints will be analyzed with the same methodology as for the primary analysis of the confirmatory binary endpoints.

Reduction in days on actual $PS \ge 2$ days per week from baseline to Week 24

The number and percent of patients who have a reduction in days on $PS \ge 2$ days per week from baseline to Week 24 will be presented for each glepaglutide treatment group and placebo

Reduction in days on actual PS \geq 3 days per week from baseline to Week 24

The number and percent of patients who have a decrease in days on $PS \ge 3$ days per weekfrom baseline to Week 24 will be presented for each glepaglutide treatment group and25 August 2022ConfidentialPage 25 of 65

placebo.

Change in duration of actual PS infusions per week from baseline

The change will be presented as descriptive statistics at Weeks 1, 2, 4, 8, 12, 16, 20, and 24.

Concentration trough levels of glepaglutide and metabolites

Concentration trough levels of glepaglutide and metabolites will be summarized descriptively. The number of non-missing observations, mean, SD, median, minimum, and maximum values will be presented by visit.

Change in plasma citrulline levels from baseline to Week 24

The change in plasma citrulline levels from baseline to Week 24 will be presented descriptively and include the number of non-missing observations, mean, SD, median, minimum, and maximum values.

Change in weekly need for parenteral micronutrients (sodium, potassium, magnesium, and calcium) from baseline to Week 24

The change in weekly need for parenteral micronutrients from baseline to Week 24 will be summarized using number of non-missing observations, mean, SD, median, minimum, and maximum values for sodium, potassium, magnesium, and calcium.

For a given visit the parental micronutrients content will be derived from the eDiary values recorded during in valid 7-day period used for deriving the actual weekly PS volume.

Actual PS intake of micronutrients will be used for the analysis involving PS content. Each of the 4 micronutrients will be summarized separately (for sodium, potassium, magnesium, and calcium).

Change in PROs (SBS-I and EQ-5D-5L) from baseline to Week 24

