The risk difference with 95% confidence intervals (using the Miettinen and Nurminen estimation method) will be estimated to quantify the uncertainty of the treatment comparison between placebo and glepaglutide 10 mg OW, placebo and glepaglutide 10 mg TW, and placebo and either of the glepaglutide groups (glepaglutide total); no formal hypothesis testing will be performed. This comparative analysis will be done for AEs leading to treatment discontinuation, AEs leading to trial withdrawal, SAEs, prespecified AESIs, other safety areas of interest and AEs occurring in \geq =5% of patients treated with glepaglutide (10 mg once weekly or 10 mg twice)

weekly). The result will be presented graphically with a dot plot in the left panel illustrating the event rates by treatment group (e.g., glepaglutide 10 mg once weekly and placebo) and a forest plot in the right panel presenting the corresponding risk difference and confidence intervals.

As a separate table, Symptoms of Injection Site Reactions will be presented with patient counts, percentages, number of events, and adverse event rate for injection site reactions including spontaneous pain, pain on palpitation, itching, redness, oedema, induration/infiltration, and other. The above symptoms are captured for AEs with a Tick mark for 'study treatment injection site reaction' in the eCRF (AE form).

The following patient listings will be provided as tables:

- Deaths
- Serious AEs
- AEs Leading to Trial Withdrawal
- AEs Leading to Treatment Discontinuation
- AEs Leading to Treatment Pause
- AESIs
- AESIs Details on Neoplasms
- Other Important Events

A listing of all TEAEs will be provided.

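### Wald 95% intervals for the weaned-off key secondary endpoint under-cover, and sit too low, if the placebo weaning rate is at or near zero

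*SAP*

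**What the plan says.** For the first key secondary endpoint, SAP 3.2 estimates the difference in response rates with Mantel-Haenszel weights over the two baseline-volume strata. The difference is "presented with 95% confidence intervals (using the Wald estimation method"). CMH provides the test. If a stratum has zero counts, the SAP drops the stratification but names no other interval, so Wald still applies. For the fourth key secondary endpoint, weaned off at Week 24, the SAP states: "The same analysis method will be applied as well".

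The method travels further. SAP 3.4 has weaning by prescribed volume "analyzed in a similar manner as the weaned off endpoint based on actual PS volume (fourth key secondary endpoint"). SAP 3.5 says of the reductions of at least 2 or 3 PS days that "these endpoints will be analyzed with the same methodology as for the primary analysis of the confirmatory binary endpoints".

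SAP 2.6 sets the group size, "with 33-37 patients planned for each of the three treatment groups". For adverse events the SAP chooses a different interval (section 7.2): "The risk difference with 95% confidence intervals (using the Miettinen and Nurminen estimation method").

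**The concern.** The Wald interval uses the unpooled variance at the observed proportions. An arm with 0 events therefore contributes zero variance, as if its rate were known exactly. Complete weaning is a demanding outcome. Patients enter needing PS at least 3 days a week, and discontinuation or missing data counts as non-response. A placebo count of 0 out of about 36 is thus plausible, although nothing in the documents establishes it.

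What is at stake is the interval that readers will use to judge the size of the weaning effect on an endpoint in the confirmatory hierarchy. If it misses more often than stated, and mostly on one side, it understates how large the benefit could be. With no events in either arm it prints 0 to 0, which claims certainty from 72 patients.

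**Working it through.** **The plan's own figures.** The documents give no rate, power or coverage for weaning. Their only related calculation is power for the primary endpoint. At N = 108 (SD 2.62, differences 2.2 and 2.0 L/week, two-sided 0.025 each), the power to succeed with either regimen recomputes as 95.3% (t) or 95.8% (normal) against the stated 95%. This confirms 36 per arm as the working size.

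**Inputs.** From the SAP: n = 36 per arm (33 and 37 also run), Wald 95%, missing data as non-response so denominators stay whole. Assumed: all event rates.

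**Formulas.** For x/n active and y/n placebo events, with p1 = x/n and p2 = y/n:
- Wald: (p1 − p2) ± 1.96 × √[p1(1−p1)/n + p2(1−p2)/n].
- Miettinen-Nurminen: invert the score statistic with constrained maximum-likelihood rates and the factor N/(N−1), where N = 2n.
- Exact coverage: add the binomial probabilities of every table whose interval contains the true difference.

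**Single tables, placebo 0/36.** For 5/36, p1 = 0.1389 and SE = √(0.1389 × 0.8611/36) = 0.0576, so Wald is 0.1389 ± 0.1130.

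| Active events | Wald (points) | Miettinen-Nurminen (points) | Wald upper limit lower by |
|---|---|---|---|
| 0 | 0 to 0 | −9.8 to 9.8 | 9.8 |
| 2 | −1.9 to 13.0 | −4.5 to 18.3 | 5.3 |
| 5 | 2.6 to 25.2 | 3.5 to 28.8 | 3.6 |
| 8 | 8.6 to 35.8 | 11.4 to 38.2 | 2.4 |

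At 2 events Wald is too narrow (about 15 points wide against 22.8). At 8 events the widths are 27.2 and 26.8, so only the location differs.

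**One coverage cell by hand: active 10%, placebo 0%.** The Wald upper limit is 0 at 0 events and 8.1 points at 1 event, so both tables lie below the true 10 points. Their probabilities are 0.90^36 = 2.25% and 36 × 0.10 × 0.90^35 = 9.01%, together 11.3%. The lower limit passes 10 points only from 9 events (0.8%). Coverage is 88.0%; Miettinen-Nurminen gives 95.4%. At 14% vs 0% the figures are 88.8% and 97.3%.

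**Average over active rates 10-20% (steps of 0.1 point), n = 36.**

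| Placebo rate | Wald | Miettinen-Nurminen |
|---|---|---|
| 0% | 91.4% | 95.4% |
| 1% | 91.9% | 95.3% |
| 3% | 93.0% | 94.9% |
| 5% | 93.8% | 94.8% |

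- At placebo 0% the range over the grid is 85.3-94.6% for Wald and 93.7-97.5% for Miettinen-Nurminen.
- Wald lies wholly below the truth in 7.6% of trials and above it in 1.1%; Miettinen-Nurminen in 1.4% and 3.2%.
- The 0 vs 0 table does not drive this average: given at least one event, Wald still averages 91.9%.
- With 33 and 37 per arm (placebo 0%), Wald / Miettinen-Nurminen are 90.8 / 95.8% and 91.5 / 95.4%.
- Mantel-Haenszel-weighted Wald with two strata (18+18 or 12+24 per arm, equal rates) gives 91.1%.

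**Lowest rates.** At 5% vs 0% Wald covers 84.0%, and at 3% vs 0% 66.5%. These cells are driven by the 0 vs 0 table (0.95^36 = 15.8% and 0.97^36 = 33.4%). Given at least one event, Wald covers 99.8% and 99.9% there.

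**Where Wald is acceptable.** Coverage is 94.4% at 8% vs 0% and 93.9% at 10% vs 3%. For mid-range rates (active 30-69%, placebo 20-40%) Wald averages 94.1-94.2% and Miettinen-Nurminen 95.0-95.1%.

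**The case against.** - **The premise is not in the documents.** No weaning rate is stated for any arm, and at placebo 3-5% Wald is close to nominal. This stands; the finding is conditional.
- **No decision changes.** CMH is the test. In every x/36 vs 0/36 table from 0 to 12 events, Wald and Miettinen-Nurminen agree on whether zero is excluded (both exclude it from 4 events on). This stands and keeps the point minor.
- **The misses fall where no effect would be claimed.** At placebo 0% and active 10-20%, given at least 4 active events, Wald covers 98.6% and Miettinen-Nurminen 95.8%. The figures are right, but an interval is judged by its coverage over all trials, and this interval will be reported whatever the count.
- **The direction is conservative for the drug, and the lower limit is not uniformly too low.** With placebo at 0/36, Wald's lower limit is above Miettinen-Nurminen's at 1-3 events, equal at 4 and below from 5. This agrees with the split between too narrow at low counts and too low at higher ones. An interval that understates possible benefit is still miscalibrated.
- **Wald was chosen deliberately.** SAP section 9 records that the interval and test were specified because these are confirmatory endpoints. That is a reason to settle the interval before unblinding; it does not improve the coverage.

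**Conclusion.** The concern holds, as a minor one. If the true placebo weaning rate is 0-1% and the active rate 10-20%, the nominal 95% Wald interval falls about 3-4 points short on average, with the misses mostly below the true difference. At placebo 5% the shortfall is about 1 point. The result rests on assumed event rates and, for the stratified check, on equal rates across strata. It is stable across 33-37 patients per arm. The zero-count rule does not repair it, because it changes the weighting and not the interval. Endpoints with mid-range response rates are hardly affected.

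**What to change.** In SAP 3.2, replace the Wald interval with the Miettinen-Nurminen score interval already named in SAP 7.2. Use it stratified with Mantel-Haenszel weights, and unstratified when the zero-count rule applies. Apply it to the primary composite estimand of all binary key secondary endpoints and to the endpoints in SAP 3.4 and 3.5 that borrow the method. Keep CMH as the test.

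Leave the supplementary treatment-policy estimand as it is. There the SAP states: "The test statistics based on the MI will be combined by applying Rubin's rule after Wilson-Hilferty transformation". Rubin's rule pools estimates with standard errors, which a score interval does not supply. The primary and supplementary intervals would then differ in method, and a footnote should say so.

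The cost is one sentence in SAP 3.2 before unblinding, plus specification and validation of the stratified form, since SAP 7.2 mentions no stratification. The downside is wider intervals when events are rare (22.8 against about 15 points at 2/36 vs 0/36) and conservative coverage at the lowest rates (up to 99.6% at 3% vs 0%).
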